12.0 Participant Information

12.1 Subject Population:

DoD beneficiaries aged 45 years and older who will be receiving a TKA, on either knee.

12.2 Age Range:

Check all the boxes that apply. If the age range of potential subjects (specimens, records) does not match the range(s) selected, please specify in the text box.

- 0-17
- 18-24
- 25-34
- 35-44
- 45-54
- 55-64
- 65-74
- 75+

12.3 Gender:

- Male
- Female
- Other

12.4 Special categories, check all that apply

- Minors /Children
- Students
- Employees - Civilian
- Employees - Contractor
- Resident/trainee
- Cadets /Midshipmen
- Active Duty Military Personnel

- Wounded Warriors
- Economically Disadvantaged Persons
- Educationally Disadvantaged Persons
- Physically Challenged (Physical challenges include visual and/or auditory impairment)
- Persons with Impaired Decisional Capacity
- Prisoners
- Pregnant Women, Fetuses, and Neonates
- Non-English Speakers
- International Research involving Foreign Nationals - Headquarters Review is necessary

You must also consider the requirements of DoDI 3216.02, Enclosure 3, paragraph 7.e.

12.5 Inclusion Criteria:

Order Number	Criteria
1	
 • Aged 45 years or older • Planned to undergo primary total knee arthroplasty • Able to speak, read, and understand English • Willing to complete a study questionnaires • Willing to bring in their medications to be counted • DoD beneficiaries • No allergy to lidocaine • Not fearful of needles

12.6 Exclusion Criteria:

Order Number	Criteria
1	
 • Chronic opioid users (daily use of prescribed opioids for at least 90 days) • Diagnosed with Fibromyalgia • Non-English speaking • Unable to read English • Unable to understand English • Pregnant • Allergy to lidocaine/sulfite allergy • Not willing to complete study questionnaires • Not willing to bring in their medications to be counted • Not a DoD beneficiary • Fearful of needles

13.0 Recruitment and Consent

13.1 Please describe the recruitment process, including how subjects will be identified and selected for the study.

A HIPAA Waiver will be used to access MHS Genesis to obtain all joint surgeons case lists for those patients scheduled for TKA. The principal investigator will review case lists to identify name, type of surgical procedure (i.e., TKA), date

scheduled for surgical procedure, and phone. Patients scheduled for a TKA within two weeks will be contacted to discuss the study. Study inclusion and exclusion criteria will be reviewed with patients who are interested in participation to ensure they are eligible. Those who are eligible will be scheduled an appointment with the principal investigator before TKA surgery, ideally at their pre-op visit (consent will not be on the same day as the surgery), to review consent documents and answer any questions. A copy of the consent documents may be emailed (if email address is provided) to the patient prior to the appointment to allow him/her to review them in advance.

13.2 Compensation for Participation:

No

13.3 Please describe the pre-screening process. If no pre-screening, enter Not Applicable in the text editor

No

13.4 Consent Process: Revised Common Rule, Section 219.116: General requirements for informed consent, whether written or oral, are set forth in this paragraph and apply to consent obtained in accordance with the requirements set forth in paragraphs (b) through (d) of this section. Broad consent may be obtained in lieu of informed consent obtained in accordance with paragraphs (b) and (c) of this section only with respect to the storage, maintenance, and secondary research uses of identifiable private information and identifiable biospecimens.

Are you requesting a waiver or alteration of informed consent?

Yes No

Please explain the consent process:

Patients will be recruited through use of a HIPAA Waiver to access joint surgeon case lists. Patients scheduled for a TKA will be contacted by the principal investigator and informed of the study. Those who desire to participate will have study inclusion/exclusion criteria reviewed to determine eligibility. Those eligible will be scheduled a consent appointment. The investigator will offer to email (or provide by hard copy) consent document to review prior to the appointment. When patients return for consenting, they will be taken to a private room (clinic exam room or private room in the PACU) to conduct the consent procedures. Consent documents will be reviewed with patients and any questions asked will be answered. Patients who desire to enroll in the study will sign the consent documents. The investigator will sign the consent documents, then provide a copy to the patient. During the recruitment and consenting phase, the PI or AI will not be in military uniform or have their rank visible.

13.5 DoDI 3216.02 requires an ombudsman to be present during recruitment briefings when research involves greater than minimal risk and recruitment of Service members occurs in a group setting. If applicable, you may nominate an individual to serve as the ombudsman.

N/A
 Propose ombudsman

13.6 Withdrawal from Study Participation:

Explain the process for withdrawal and specify whether or not the subjects will be given the opportunity to withdraw their data or specimens in the event they wish to withdraw from the study

At any point in the study participants can self-withdrawal from the study if they have a poor response to the injections, are unable to tolerate all injections, not willing to complete questionnaires, intraoperative complications (pulmonary embolism, deep vein thrombosis, surgical site infection, multiple or other), not willing to bring in their medications or if they choose to no longer participate in the study. However, any data collected prior to withdrawal will still be analyzed.

14.0

Risks and Benefits

14.1

Risks of Harm:

Identify all research-related risks of harm to which the subject will be exposed for each research procedure or intervention as a result of participation in this study. Consider the risks of breach of confidentiality, psychological, legal, social, and economic risks as well as physical risks. Do not describe risks from standard care procedures; only describe risks from procedures done for research purposes

Risk of breach of confidentiality. Other risks of harm include allergy to the medication used in the trigger point injection, pain, bleeding, injury to neurovascular structures, and infection. Being selected for the sham can potentially increase a patient's risk for pain.

14.2

Measures to Minimize Risks of Harm (Precautions, safeguards):

For each research procedure or intervention, describe all measures to minimize and/or eliminate risk of harms to subjects and study personnel

Risk is limited by coding the data, security limiting access of the data set to investigators, password protected files, and lock and key.

Injections will be performed by a trained provider under an aseptic technique by prepping the site with alcohol swabs. All injection sites will be marked utilizing landmarks to identify each muscle belly. The plunger will be retracted prior to injecting medication to ensure needle placement is not within a vascular structure. One needle and plunger will be used for each muscle belly to limit risk of infection. After completion of all injections the injection site will be cleaned with alcohol swabs and a bandage will be applied.

14.3

Confidentiality Protections (for research records, data and/or specimens):

Describe in detail the plan to maintain confidentiality of the research data, specimens, and records throughout the study and at its conclusion (e.g., destruction, long term storage, or banking). Explain the plan for securing the data (e.g., use of passwords, encryption, secure servers, firewalls, and other appropriate methods). If data will be shared electronically with other team members/collaborators outside the institution, describe the method of transmission and safeguards to maintain confidentiality. Explain whether this study may collect information that State or Federal law requires to be reported to other officials or ethically requires action, e.g., child or spouse abuse

Risk is limited by coding of the data set, password protection, locked cabinet /drawer, and security limiting access of the data set to investigators.

14.4

Potential Benefits:

Describe any real and potential benefits of the research to the subject and any potential benefits to a specific community or society

If the individuals in the research are considered experimental subjects (per 10 USC 980), and they cannot provide their own consent, the protocol must describe the intent to directly benefit all subjects

The potential benefits of this study include a decrease in pain levels following TKA. This could result in decreased risk for opioid use disorder. Also, this may secondarily improve recovery and allow for easier participation in physical therapy.

14.5

Privacy for Subjects:

Describe the measures to protect subject's privacy during recruitment, the consent process, and all research activities, etc.

All consents and other information will be stored on a CAC enable computer that is password protected only accessible to investigators. All consents will be performed by either the PI and/or AI without official military uniforms or ranks displayed in a private exam or PACU room. Hard copy consent documents will be stored in a locked drawer, separate from other study documents, and saved for at least six years after study closure. After this period, the hard copy, and electronic study documents will be destroyed by shredding and/or files deleted.

14.6

Incidental or Unexpected Findings:

Describe the plan to address incidental findings and unexpected findings about individuals from screening to the end of the subject's participation in the research. In cases where the subject could possibly benefit medically or otherwise from the information, state whether or not the results of screening, research participation, research tests, etc., will be shared with subjects or their primary care provider. State whether the researcher is obligated or mandated to report results to appropriate military or civilian authorities and explain the potential impact on the subject

If any incidental unexpected findings are identified by the investigators during the medical record review (i.e., capturing medical or surgical history data), he/she will inform the participant and his/her primary care provider to facilitate follow-up.

15.0

Study Monitoring

15.1 Your study requires either Data and Safety Monitoring Plan (DSMP) or a Data and Safety Monitoring

Board (DSMB).

- DSMP
- DSMB
- Both
- Not Applicable

16.0**Reportable Events**

16.1 Reportable Events: Consult with the research office at your institution to ensure requirements are met. Describe plans for reporting unexpected adverse events and unanticipated problems. Address how unexpected adverse events will be identified, who will report, how often adverse events and unanticipated problems will be reviewed to determine if any changes to the protocol or consent form are needed and the scale that will be used to grade the severity of the adverse event.

Consult with the research office at your institution to ensure requirements are met

- Describe plans for reporting expected adverse events. Identify what the expected adverse events will be for this study, describe the likelihood (frequency, severity, reversibility, short-term management and any long-term implications of each expected event)
- Describe plans for reporting unexpected adverse events and unanticipated problems. Address how unexpected adverse events will be identified, who will report, how often adverse events and unanticipated problems will be reviewed to determine if any changes to the research protocol or consent form are needed and the scale that will be used to grade the severity of the adverse event

Pain – pain is anticipated given the type of intervention. However, pain is temporary and will improve after the local anesthetic takes effect.

Bleeding – another rare complication of trigger points. If a vascular structure is infiltrated the injection will be halted. Once the needle is removed will apply direct pressure for 3-5 minutes to ensure no continued bleeding. Likelihood of accessing vascular structures is minimal due to the location of arteries as they relate to musculature aimed at injecting.

Infection – very low risk for infection following trigger point injection, <0.05% of adverse side effects are reported. If infection takes place, then the patient will be treated with antibiotics. If infection includes an abscess will treat with incision and drainage.

Adverse events such as infection, damage to vascular structures that cause hematoma and excessive bleeding, injection of lidocaine into the blood stream are identified will be reported to the IRB. These adverse events will be monitored for during each visit through visually inspecting the injection sites and completing a neurovascular evaluation. The patient may also verbally inform the principal investigator of any of these potential adverse effects. The IRB will be notified by completing and submitting an eIRB Reportable Event Form (serious adverse event, unanticipated problem) or reporting at the time of continuing review (all others). The form will be routed to the DGMC C&T Board. The DGMC HRPP staff regularly monitor C&T Board notifications; they will notify the institution's HRPO of the reportable event by email, telephone, or in-person until it has been received and acknowledged. If any adverse event takes place the design of this study will be examined and determine if research protocol needs to be revised.

17.0**Equipment/non-FDA Regulated Devices**

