those in the sham injection group an S. The study participants will not know which study group they will be assigned to. An equal number of participants will be included in each group (ie, trigger point injection vs. sham injection).

Step 3a: (Trigger point injection group) The principal investigator will identify relevant structures to include the vastus medialis, vastus lateralis, medial, and lateral gastrocnemius muscle bellies by utilizing anatomical landmarks. Once those structures are identified, each area will be prepped in an aseptic fashion with alcohol swabs. Two injections will be made in each muscle belly. Each injection will include 0.5 mL of 1% lidocaine without epinephrine. A total of eight injections will be administered with a total of 4 mLs of 1% lidocaine without epinephrine using a 1 ½" 25-gauge needle. A separate needle and syringe will be utilized for each of the four muscle bellies. Careful consideration to avoid neurovascular structures will be taken by retracting the plunger to ensure needle placement is outside vascular structures with each injection. A blind will be placed between the patient and the needle in order for the patient not to witness the injection, which is the same protocol as the sham injection. The blind used will be a drape or other soft item held by a person not involved with the study to obscure the vision of the subject during the injection and allow the investigator to use both hands to safely conduct the injection and aspiration procedure. The local anesthetic will be massaged into the area to ensure the medication disperses thoroughly into the muscle belly. After the needle is removed, the area will be cleaned with alcohol swabs and a bandage will be applied. This will be completed on POD 0 (ie, the day of the TKA procedure). Within the informed consent the consenting verbiage will ensure that the participants will not be able to identify injection technique that will identify whether they are in the sham or experimental group.

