on the region that best represents their pain and writing the number (a whole number) on the form; scores range from 0 (no pain) to 100 (severe intolerable pain). The Opioid Use questionnaire will be used to document average opioid use following discharge. Both questionnaires will be completed by all participants at POD1, week 2 and week 6 visits. The VAS will be given to the participant with the intake form that is provided by the orthopedic technician, and the investigator will provide the Opioid Use questionnaire to the participant during the visit, and review the MAR Summary to obtain and calculate the total MME from POD0 to POD1 using MDCalc . Prior to ending the visit, the investigator will ask participants to bring in their opioids to be physically counted at their week 2 and week 6 visits.

Step 6: The investigator will provide a reminder phone call 1-2 days prior to the week 2 and week 6 appointments to ensure participants remember to bring in their medication.

Step 7: Participants return for the week 2 and week 6 visits. They are given VAS and Opioid Use questionnaires to complete, and opioid medication is counted. Once opioids have been accounted for, MME will be calculated.

10.2 Data Collection:

Describe all the data variables, information to be collected, the source of the data, and how the data will be operationally measured.

Injection type: Dichotomous variable. Trigger point or sham injection.

Visual analogue scale: Discrete variable. Will be scaled from 0 (no pain) to 100 (severe intolerable pain) and will be measured at POD1, week 2, and week 6. The VAS will be presented to the participant on paper.

Morphine milligram equivalent (MME): Discrete variable. Will be measured from POD 0 to POD1, then a total MME will be calculated from POD1 to week 2 and week 2 to week 6. This will be calculated utilizing the MME calculator on MDCalc.

Block: Categorical variable. Spinal, adductor or femoral nerve block determined by anesthesiology.

Age: Continuous variable. Age stated in years at time of surgery as stated in EHR.

Prior Pain Medications: Categorical variable. Obtained from EHR.

Discharge disposition: Dichotomous variable. Discharge to skilled nursing facility or home, discharge disposition will be reviewed in the discharge summary.

Active Duty, Dependent, Retiree: Categorical Variable.

Sex: Categorical (male, female). Obtained from EHR.

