11.0 Statistical/Data Analysis Plan

11.1 Data Analysis Plan and Statistical Considerations:

List the statistical methods to be used to address the primary and secondary objectives, specific aims, and/or research hypotheses. Explain how missing data and outliers will be handled in the analysis. The analysis plan should be consistent with the study objectives. Include any subgroup analyses (e.g., gender or age group). Specify statistical methods and variables for each analysis. Describe how confounding variables will be controlled in the data analysis.

Demographic (age at time of surgery, BMI, sex, active duty/dependent/retiree status), medical (ICD code, nicotine use, history of diabetes, prior pain medications), laterality of the TKA (left or right), discharge disposition, and anesthetic block type (spinal, adductor, or femoral nerve block) data will be summarized overall and as a function of injection group using descriptive statistics (eg, mean, standard deviation, median, minimum, maximum, frequency, percentages) and 95% confidence intervals to describe the sample. Appropriate inferential statistics (eg, independent samples t tests, chi square tests) will be performed to determine if there are statistically significant differences in any of these variables between the two injection groups. If so, multivariable techniques (eg, ANOVA or regression) including these potentially confounding variables in the analyses and/or stratification will be undertaken.

VAS pain scores and the dosage (MME) of opioids will be evaluated in patients as a function of injection type (ie, trigger point injection vs. sham injection) at each time point. Data will be assessed for normality and homogeneity of variance to determine whether parametric (eg, independent samples t tests, repeated measures ANOVAs) or nonparametric (eg, Wilcoxon Mann Whitney tests, Skillings-Mack tests) methods are appropriate.

In addition, the number of patients with a VAS>40 (indicating a “significant” level of pain) will be calculated and compared in each group and at each time point using the chi-square test (or the Fisher’s Exact test if assumption regarding minimum expected cell counts is not met) as well as McNemar’s tests.

The critical alpha level will be set at .05. Missing data will be handled using the “pairwise deletion” method; this method still includes patients with some missing data in the analyses when possible.

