11.5 Please provide a justification for your sample size

We used G*Power 3.1 (Dusseldorf Germany) to perform sample size calculations for our study. We designed these calculations using the primary outcome measure (ie, VAS pain scale rating in each injection group) which will be statistically compared using the independent samples t test or its nonparametric equivalent (ie, the Wilcoxon Mann Whitney test) if the assumptions for the independent samples t test (ie, normality and homogeneity of variance) are not met.

Using the more conservative Wilcoxon Mann Whitney test (Type 1 error/alpha level=.05 (two tailed) and power=.80), a sample size of 30 (ie, 15 in the trigger point group and 15 in the sham group) would allow us to detect a statistically significant difference in VAS pain scale ratings if a “large” effect size of 1.1 was obtained. A “large” effect size of 1.1 corresponds to an average difference (delta) in VAS scores between groups of ≥ 28 units and an average standard deviation in each group of ≤ 25 units. This standard deviation is similar to Mayoral et al. (2013) who reported an average standard deviation of 25 units for the VAS at the 1 month follow up. Note that Mayoral et al. (2013) did not report VAS scores on POD1, although their average difference (delta) in VAS scores at 1 month was smaller than 28 units.

If up to 5 patients (eg, 30%) per group drop out of the study, a lower sample size of 20 (ie, 10 in the trigger point group and 10 in the sham group) would allow us to detect a statistically significant difference in VAS pain scale ratings if a larger effect size of 1.4 was obtained. This “larger” 1.4 effect size corresponds to an average difference (delta) in VAS scores between groups of ≥ 35 units and an average standard deviation in each group was ≤ 25 units (again using the more conservative Wilcoxon Mann Whitney test (Type 1 error/alpha level=.05 (two tailed) and power=.80)).

In summary, our aim of including at least 10-15 patients per group would allow us to statistically detect a “large” effect of trigger point injections (relative to sham injections) on VAS pain ratings assuming our standard deviations were \leq to the standard deviations in VAS pain scales reported by Mayoral et al. (2013). In addition, if statistically significant differences are not found, the data from our

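### Poor response and intolerance are listed reasons to leave the study, no VAS is planned afterwards, and pairwise deletion leaves the week 2 and week 6 comparisons at risk of outcome-related dropout bias

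*Combined protocol and SAP*

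**What the plan says.** - **Withdrawal (13.6).** Participants may choose "self-withdrawal from the study if they have a poor response to the injections, are unable to tolerate all injections", along with several other reasons and a general right to leave. The section adds: "However, any data collected prior to withdrawal will still be analyzed". It does not say that someone who leaves for either of these two reasons will still be asked for VAS.
- **Timing (10.1, Steps 3a and 5).** On the injections: "This will be completed on POD 0 (ie, the day of the TKA procedure". On VAS and opioid use: "Both questionnaires will be completed by all participants at POD1, week 2 and week 6 visits". No VAS is scheduled before POD1.
- **Missing data (11.1).** "Missing data will be handled using the “pairwise deletion” method", with the explanation that "this method still includes patients with some missing data in the analyses when possible". This is the only missing-data rule. The plan states no intention-to-treat set, no sensitivity analysis for informative dropout and no comparison of withdrawals between groups.
- **Binary outcome (11.1).** "the number of patients with a VAS>40 (indicating a “significant” level of pain) will be calculated and compared in each group", at each time point. How a participant who has withdrawn is counted is not stated.
- **Dropout (11.5).** "If up to 5 patients (eg, 30%) per group drop out of the study", the plan recalculates the detectable effect at 10 per group. Dropout is treated only as lost sample size.

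**The concern.** A poor response to a pain injection is, in substance, a high pain score, which is the primary outcome. Section 13.6 thus names the outcome as a reason to leave, while 11.1 relies on an analysis that is valid only when leaving has nothing to do with the outcome. Because the injection is given once, leaving cannot spare the participant further study treatment. It only ends the pain scores.

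The direction of any bias depends on who leaves:

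- If mainly sham participants with high pain leave, the remaining sham group looks better and a real effect shrinks.
- If mainly trigger point participants with high pain leave, an ineffective injection can look beneficial.
- If equal fractions with similar score distributions leave, the difference does not move.

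Equal loss is not assured. Only the trigger point group receives eight intramuscular injections with volume, and section 14.1 says that being in the sham group may increase the risk of pain. At 10 to 15 per group a few such losses matter, and scores that were never collected cannot be recovered.

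**Working it through.** **1. The plan's own figure.** Inputs from 11.5: Wilcoxon Mann Whitney, two-sided 0.05, power 0.80, effect sizes 1.1 and 1.4. With the normal-parent efficiency 3/π, the effective n per group is n × 3/π, the noncentrality is d × √(effective n / 2), and df is 2 × effective n − 2.

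- n = 15, d = 1.1: effective n 14.32, noncentrality 1.1 × √7.16 = 2.94, df 26.6, power 0.810.
- n = 10, d = 1.4: effective n 9.55, noncentrality 1.4 × √4.77 = 3.06, df 17.1, power 0.822.

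Both stated sample sizes reproduce, so the point does not rest on an error there. (5 of 15 is 33%; the text says 30%.)

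**2. How far an available-case mean can move.** If the highest fraction q of one group leaves, its mean falls by SD × φ(z)/(1 − q), where z is the upper-q normal quantile. If leaving depends on POD1 VAS and the comparison is at a later visit, multiply by the between-visit correlation. With SD 25:

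| q lost from one group | Shift if leaving tracks the same visit's VAS | Shift at correlation 0.6 (× 0.6) |
|---|---|---|
| 10% | 25 × 0.1755/0.90 = 4.9 | 2.9 |
| 20% | 25 × 0.2800/0.80 = 8.7 | 5.2 |
| 33% | 25 × 0.3636/0.667 = 13.6 | 8.2 |

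The sign depends on the group that loses them. Equal q in both groups cancels.

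**3. Simulation at 15 per group.** From the plan: difference 28, SD 25, Wilcoxon test. Assumed, not in the documents: sham mean 60, scores limited to 0-100, correlation 0.6 between POD1 and the later visit, and exit decided by POD1 VAS.

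| Scenario, later visit | Difference (sham minus trigger point) | Rejection rate |
|---|---|---|
| True 28, nobody leaves | about 26 | about 0.80 |
| True 28, 10% of all participants lost at random | about 26 | about 0.77 |
| True 28, the 10% with highest POD1 VAS leave | about 22-23 | about 0.66 |
| True 0, nobody leaves | 0 | 0.04-0.05 |
| True 0, one pain cut-off applied to both groups | 0 | 0.04-0.05 |
| True 0, highest 20% of the trigger point group only leave | about 4-5 | about 0.08 |

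The full-data difference is 26 rather than 28 because scores are limited to 0-100. Across correlations 0.4 to 0.8, power in the third row is about 0.64 to 0.71.

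**4. An extreme for scale.** Assume a sham mean of 50, no limits on scores, and exit tracking the same visit's VAS. If all 5 of the 15 allowed dropouts were the worst scorers of one group, the difference would move by about 13 units and the null rejection rate would rise from 0.044 to 0.27. Losing the worst 5 of both groups leaves the difference at 0, with a rejection rate of 0.108.

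**5. POD1.** A participant who leaves after POD1 has contributed the POD1 score. One who leaves on POD0 because the injections were not tolerated has no VAS at all, so the sentence that retains earlier data does not help.

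**The case against.** Three stronger readings are tempting, and the documents do not support them.

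- **That the primary comparison is biased because failures are removed and their scores deleted.** Withdrawal is voluntary and nobody is taken out for poor response. Later scores are not collected rather than discarded, and earlier ones are analysed. The number who would leave is unknown, and may be small because only questionnaires and a pill count remain. The plan names no single primary visit, and POD1 is affected only by those who leave before it.
- **That power falls to about 0.36-0.43.** This results if the 30% of all participants with the highest POD1 VAS leave. A pooled cut-off of that kind removes on average about 7 of 15 sham participants, against the 5 per group for which the plan allows. The 10% case is the fairer illustration. There the loss beyond random dropout is about 0.77 − 0.66 = 0.11 at correlation 0.6, and 0.06 to 0.10 in a second run of the same model across correlations 0.4 to 0.8.
- **That every such withdrawal should be scored as the worst rank.** This looks good only when leavers truly are the worst. If 3 or 5 of 15 trigger point participants leave for intolerance unrelated to pain and there is no true effect, worst-rank scoring gives false-positive rates of about 0.11 and 0.29, against about 0.05 for pairwise deletion. At a true difference of 28 with 3 lost, power falls from about 0.77 to 0.11.

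The false-benefit scenario also needs unequal loss. With no true effect and participants unaware of their group, poor response should arise about equally in both. That stands, and it is why the direction is left open.

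Finally, anyone may leave for any reason, so removing two reasons from a list would change little by itself. That also stands: the useful change is the explicit request for continued VAS.

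**Conclusion.** The point holds as a risk of bias, not as a demonstrated bias. Sections 13.6 and 11.1 together allow outcome-related loss of VAS and then analyse the available cases as if the loss were unrelated to pain. Week 2 and week 6 are the exposed visits, for both VAS and VAS>40. POD1 is exposed only through POD0 leavers.

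Under the stated assumptions, a modest 10% pain-related loss costs about 4 units of a 26-unit later difference and about 0.1 of power beyond random loss. A one-sided 20% loss from the trigger point group under no effect gives a spurious 4-5 units and an error rate of about 8%. These sizes rest on the assumed sham mean, score limits, visit correlation and exit rule, none of which the documents give. With equal fractional loss there is no shift in the difference. The plan should be changed because the remedy is cheap and missing scores cannot be recovered.

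**What to change.** **Section 13.6.** State that participants with a poor response, or who do not complete all injections, remain in the study in their assigned group and are asked for VAS at POD1, week 2 and week 6. Full voluntary withdrawal remains available to anyone. This concerns measurement only and does not alter clinical care.

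**Section 11.1.**
- Analyse all participants in the group to which they were assigned.
- Record the reason for each withdrawal, and report withdrawals by group and reason.
- Keep the available-case analysis, and add a prespecified sensitivity analysis for outcome-related withdrawal, for example counting those who withdraw for poor response as VAS>40 at later visits.
- Do not make worst-rank scoring the main analysis, and do not apply it to withdrawals for intolerance.

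**Cost.** Some wording, one withdrawal-reason field and one extra analysis. The visits already exist and no more participants are needed. Classifying reasons takes judgement, and the principal investigator who gives the injections knows the group, so the reason should be recorded as the participant states it.
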